## 9.6 Changes to Concomitant Medications, Treatments/Procedures

After the subject is enrolled into the study, the investigator must instruct the subject to notify the study site about:

- Any new medications
- Alterations in dose or dose schedules for current medications,
- Any medical procedure or hospitalization that occurred or is planned
- Any nondrug therapies (including physical therapy and blood transfusions).

The investigator must document this information in the subject's case history source documents.

## **10 STUDY PROCEDURES AND ASSESSMENTS**

### **10.1 Informed Consent and Screening**

The investigator or delegate must explain the purpose and nature of the study, and have the subject read, sign, and date the IRB/IEC-approved informed consent document. The subject must sign the ICF BEFORE any study-specific procedures or assessments can be performed, including study-specific screening procedures. Additionally, have the individual obtaining consent from the subject and a witness, if applicable, sign and date the informed consent document.

The investigator or delegate must provide a copy of the signed document to the subject and place the original signed document in the subject's chart, or provide documentation as required by local regulations.

### **10.2 Description of Study Procedures and Assessments**

Study-specific procedures and assessments described here may include standard of care; other standard of care procedures performed in the clinical management of the subject are not excluded.

Detailed descriptions of assessments and procedures are provided in the MOP. The investigator is responsible for ensuring responsibilities for all procedures and assessments are delegated to appropriately qualified site personnel.

#### **10.2.1 Demographics**

Obtain demographic information including age, race, ethnicity, and sex. Refer to the MOP for details.

#### **10.2.2 Medical History and Concomitant Medications**

Fully document concomitant medications (taken within the past 30 days prior to the screening visit) and medical history (within 1 year prior to the screening visit) in the subject source documents. Throughout the subject's participation, obtain information on any changes in medical health and/or the use of concomitant medications.

Medical history and concomitant medications will be collected in the eCRF as outlined in the MOP.

#### **10.2.4 Habitual Lens Information**

At Visit 1, the subject's habitual contact lens information will be collected. Refer to the MOP for details.

#### **10.2.5 Keratometry**

Keratometry is required at Visit 1. Refer to the MOP for details.

#### **10.2.6 Autorefractometry**

Autorefractometry (OD, OS) will be performed either uncorrected or with the study contact lenses. Refer to the MOP for details.

#### **10.2.7 VA with Habitual Correction**

VA (Snellen distance; OD, OS) with the subject's habitual spectacles correction will be collected at Visit 1 and at the Exit Visit (Visit 5 or Early Exit) and is optional for Unscheduled Visit. Refer to the MOP for details.

#### **10.2.8 Fitting of Study Products with Fitting Lenses: Effectiveness Assessment**

[figure not shown]
Fitting of study products will be performed for both the test and comparator study lenses at Visit 1 per the randomization assignment. [REDACTED]

[REDACTED]

[REDACTED]

#### **10.2.10 HC/HI VA with Study Lenses: Effectiveness Assessment**

HC/HI logMAR [REDACTED] VA with study lenses will be performed at Visits 2, 3, 4, 5, and Early Exit and is optional at Unscheduled Visit. Refer to the MOP for details.

### **10.2.18 Worn Lens Collection**

Worn lenses will be collected and returned. Refer to the MOP for details.

### **10.2.19 Investigational Product Compliance**

Review subject compliance with the IP usage and adjunct product usage and collect all used and unused study IPs and other products that were dispensed.

### **10.2.20 Adverse Event Collection: Safety Assessment**

Assess and record any adverse events that are observed or reported since the previous visit, including those associated with changes in concomitant medication dosing in the subject source documents. See Section 11 for further details regarding AE collection and reporting.

### **10.2.21 Slit Lamp Biomicroscopy: Safety Assessment**

SLE of the cornea, iris/anterior chamber, and lens must be performed in both eyes before instillation of any diagnostic eye drops.

### **10.2.22 Device Deficiencies: Safety Assessment**

Assess and record any device deficiencies that are reported or observed since the previous visit. Requirements for reporting device deficiencies in the study can be found in Section 11.

## **10.3 Unscheduled Visits**

If a subject visit occurs between any regularly scheduled visit and the visit is conducted by study personnel, this visit must be documented as an Unscheduled Visit. If the subject seeks medical attention outside the clinic (for example, at an emergency room) or at the clinic but is

seen by nonstudy personnel, the investigator is to capture adverse event-related information on the adverse event form upon becoming aware.

During all unscheduled visits, the investigator must conduct the following procedures:

- Collect adverse event information
- Collect device deficiency information
- [REDACTED]
- Record changes in medical condition or concomitant medication
- Biomicroscopy
- [REDACTED]

The investigator may perform additional procedures for proper diagnosis and treatment of the subject. The investigator must document this information in the subject's case history source documents.

If during an Unscheduled Visit the subject is discontinuing the IP or discontinuing from the study, the investigator must conduct Exit procedures according to [Table 3–1](#) and [Section 10.5.3](#) as possible.

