Device Deficiency	
Inadequacy of a medical device with respect to its identity, quality, durability, reliability, usability, safety, or performance.
 
Note: This definition includes malfunctions, use errors, and inadequacy in the information supplied by the manufacturer including labelling related to the investigational medical device or the comparator.
 
Requirements for reporting device deficiencies in the study can be found in Section 11.

Enrolled Subject	
Any subject who signs an informed consent form for participation in the study.

Point of Enrollment	
The time at which, following recruitment and before any clinical investigation-related procedures are undertaken, a subject signs and dates the informed consent form.

Interventional Clinical Trial	
A pre- or postmarket clinical investigation where the assignment of a subject to a particular medical device is decided in advance by a clinical investigation plan, or diagnostic or monitoring procedures requested in the CIP are in addition to those available as normal clinical practice and burden the subject.

Investigational Product	A preventative (vaccine), a therapeutic (drug or biologic), device, diagnostic, or palliative used as a test or comparator product in a clinical trial, including a product with a marketing authorization when used or assembled (formulated or packaged) in a way different from the authorized form, or when used for an unauthorized indication, or when used to gain further information about the authorized form.
Malfunction	Failure of an investigational medical device to perform in accordance with its intended purpose when used in accordance with the instructions for use or clinical investigation plan (CIP), or investigator's brochure (IB).
Noninterventional Study	Clinical investigation that draws inferences about the possible effect of an intervention on subjects, but the investigator has not assigned subjects into intervention groups based on a protocol and has not made any attempts to collect data on variables beyond those available throughout the course of normal clinical practice and burden to the subject.  NOTE: The term “noninterventional” is synonymous with “observational.”
Nonserious Adverse Event	Adverse event that does not meet the criteria for a serious adverse event.

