## 10.5.2 Discontinuations

Discontinued subjects are individuals who voluntarily withdraw or are withdrawn from the study by the investigator after signing informed consent and after randomization.

Subject numbers of discontinued subjects must not be reused (i.e., subject replacement is not allowed).

Subjects may discontinue from study or study treatment at any time for any reason. Subjects may also be discontinued from study treatment at any time if, in the opinion of the investigator, continued treatment poses a risk to their health.

If a subject discontinues from study treatment, every effort must be made to keep the subject in the study and to continue with the study assessments as specified in the schedule of study procedures and assessments until the final visit.

For subjects discontinuing from the study, the investigator must complete all Exit procedures according to [Table 3–1](#) and [Section 10.5.3](#), if the subject is willing and able, and if in the opinion of the investigator it is safe for the subject to do so.

The investigator must document the reason for study or treatment discontinuation in the subject's case history source documents.

To ensure the safety of all subjects who discontinue early, investigators must assess each subject and, if necessary, advise them of any therapies and/or medical procedures that may be needed to maintain their health.

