## 10.5.3 Schedule of Procedures and Assessments for Subjects Discontinued from Investigational Product

Other than screen failures, if a subject discontinues from the study, the subject should undergo an Early Exit Visit. Refer to [Table 3–1](#) and the MOP for details.

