## 12.6 Safety Analyses

The safety endpoints are:

- AEs
- Biomicroscopy findings
- Device deficiencies

There are no safety hypotheses planned in this study. The focus of the safety analysis will be a comprehensive descriptive assessment of occurrence of adverse events as well as the other listed parameters.

All AEs occurring from the time a subject signs informed consent to study exit will be accounted for in the reporting. Safety analyses will be conducted using the safety analysis set on a treatment-emergent basis. Descriptive summaries (frequencies and percentages) for ocular and nonocular AEs will be presented by Medical Dictionary for Regulatory Activities Preferred Terms. AEs leading to study discontinuation, significant nonserious AEs, and SAEs will be identified. Individual subject listings will be provided, as necessary.

Individual subject listings will be provided for AEs that occur after signing informed consent but prior to exposure to IP.

Each biomicroscopy parameter will be tabulated by its grade. For each biomicroscopy parameter, frequencies and percentages of eyes that experience an increase of  $\geq 2$  grades from baseline (last assessment prior to study lens exposure) to any subsequent visit within the same period will be presented. A supportive listing will be generated which will include all biomicroscopy data from all visits within the same period for those eyes experiencing the  $\geq 2$  grades increase.

Two listings for device deficiencies, prior to exposure to study contact lenses and treatment-emergent, will be provided. Additionally, each device deficiency category will be tabulated.

No inferential testing will be conducted for the safety analyses.

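### Do Sections 10.3 and 10.5.2 give sites conflicting instructions, in a way that affects the results, for a subject who stops a study lens?

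*Protocol*

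**What the plan says.** Section 10.3 (Unscheduled Visits) has one rule for two events: "If during an Unscheduled Visit the subject is discontinuing the IP or discontinuing from the study, the investigator must conduct Exit procedures". It refers to Table 3-1 and Section 10.5.3 and limits the duty to what can be done.

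Section 10.5.2 (Discontinuations) treats the events separately. For lens stoppers: "If a subject discontinues from study treatment, every effort must be made to keep the subject in the study". Such a subject is meant to stay on the visit schedule through the last visit. For leavers: "For subjects discontinuing from the study, the investigator must complete all Exit procedures". It also requires the reason for either kind of stopping to be documented in the source records.

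Section 10.5.3 is headed for subjects discontinued from the investigational product, yet its body says only that "if a subject discontinues from the study, the subject should undergo an Early Exit Visit", and sends the reader to Table 3-1 and the manual of procedures (MOP).

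Three other places bear on the point:

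- Section 10.2.7 says that acuity with habitual spectacles "will be collected at Visit 1 and at the Exit Visit (Visit 5 or Early Exit) and is optional for Unscheduled Visit", so an exit visit is either Visit 5 or an Early Exit.
- The Glossary describes an investigational product as something "used as a test or comparator product in a clinical trial", so each of the two lenses is one.
- Section 12.6 says that "AEs leading to study discontinuation, significant nonserious AEs, and SAEs will be identified".

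**The concern.** Read quickly, Section 10.3 exits a subject whom Section 10.5.2 wants kept, and the section that should settle the matter has a heading for one group and a rule for the other. In a crossover the question is sharper. If each lens is an investigational product, the visible text does not say whether giving up the first lens ends participation or leads on to Visit 4 and the second lens.

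If sites chose differently, the same event would be an exit at one site and a retained subject at another. Period 2 data would then exist for some early stoppers and not for others. There is no replacement of subjects (Section 10.5.2) and no imputation (Section 12.5), and stopping because of the lens could be informative. The set of adverse events labelled as leading to study discontinuation might also vary by site.

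**Working it through.** **1. How many subjects could be involved.** Inputs from Section 8: 74 completers, 5% screen failure, 5% discontinuation, about 82 enrolled.

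- Enrolment: 74 / (0.95 × 0.95) = 81.99, rounded up to 82. This reproduces the plan's figure.
- Randomised: 82 × 0.95 = 77.9, about 78.
- Discontinued: 77.9 × 0.05 = 3.9, about 4.
- Completed: 77.9 − 3.9 = 74.0.

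The documents do not divide the 4 into lens stoppers and study leavers. Section 10.3 reaches a lens stopper only at an unscheduled visit, and the two sections pull apart only if that subject is willing to stay. The affected group is therefore a part of about 4, and may be empty. This assumes that the 5% rate covers lens stoppers as well as leavers.

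**2. Whether the instructions exclude each other.**

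| Section | Event | Instruction |
|---|---|---|
| 10.3 | Lens stopped, or study left, at an unscheduled visit | Carry out Exit procedures as far as possible |
| 10.5.2 | Treatment stopped | Try to retain; scheduled assessments to the final visit |
| 10.5.2 | Study left | Exit procedures |
| 10.5.3 | Study left (body); product stopped (heading) | Early Exit Visit |

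The first row lists procedures for one visit and does not say that participation ends. The second row governs later visits. Both can be carried out for the same subject. The final scheduled visit is Visit 5, in Period 2, so Section 10.5.2 does carry a Period 1 stopper forward. What the visible text leaves open is whether the second lens is dispensed.

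**3. What the primary analysis loses under each reading.** The endpoint is Day 30 binocular distance acuity with the study lens (Table 6-1).

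| Case | Day 30, first lens | Day 30, second lens | Pair? |
|---|---|---|---|
| Stops in Period 1, exits | none | none | no |
| Stops in Period 1, retained, second lens worn | none | present | no |
| Stops in Period 1, retained, second lens not worn | none | none | no |
| Stops in Period 2, exits or retained | present | none | no |

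No reading creates a pair. At the plan's rates there are about 74 pairs whichever section a site follows. Only an unpaired Period 2 value can depend on the reading. Such a value informs the lens difference mainly through comparison between subjects, while about 74 within-subject differences carry the estimate.

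**4. A tempting calculation that does not apply.** If 4 of 78 subjects were missing and their lens difference were worse by an assumed 0.05 to 0.20 logMAR, the mean would shift by 4/78 × 0.05 = 0.003 to 4/78 × 0.20 = 0.010, against the margin of 0.05. Those pairs are missing under every row of the table, so this is the cost of ordinary dropout and not of the wording.

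**5. Safety.** Section 12.6 undertakes to identify adverse events leading to study discontinuation. It specifies no rate for them, sets no hypothesis and runs no test. The term used there is the one that Section 10.5.2 already distinguishes from stopping treatment.

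**The case for a change.** The best case for acting is that these are two firm duties placed on sites, in unredacted text, and that reconciling them would cost a few lines. The combined reading in step 2 is nowhere spelled out. Section 10.2.7 equates an exit visit with Visit 5 or Early Exit, and Section 10.5.3 ties Early Exit to leaving the study, so running exit assessments and then retaining the subject is something sites must work out for themselves. Section 9.3 uses treatment to mean a lens sequence, so stopping treatment in Section 10.5.2 might mean both lenses. The situation is also foreseeable: Section 11.1 defines a significant nonserious event partly by stopping lens wear for at least two weeks.

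Much of this stands as a comment on drafting. The heading and body of Section 10.5.3 do not match, and Section 10.3 is loosely worded. Two parts do not carry the weight. The Period 2 question may be answered in the MOP or in blacked-out parts of Table 3-1, neither of which can be read here, so its absence from the visible text is not evidence of a gap. Different handling between sites is a possibility rather than something the documents show, and the required reason for stopping, together with visit dates in the source records (Section 13.2), lets analysts tell the two events apart and place them in a period.

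**Conclusion.** The inconsistency is real but clerical. Sections 10.3, 10.5.2 and 10.5.3 should be brought into line when the text is next revised. Which handling is right is for the sponsor, and this review takes no view on it.

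No change to the design, analysis sets, model or sample size follows. Followed as written, the plan still supports a sound noninferiority conclusion and a sound descriptive account of safety. At most a part of about 4 in 78 subjects is touched. The pairs behind the primary comparison do not depend on the reading, and no specified safety figure moves.

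This rests on discontinuation near the planned 5%, on that rate including lens stoppers, and on early stoppers having no Day 30 value on the abandoned lens. Discontinuation well above 5% would enlarge the affected group, but would still create no pairs.

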## 10.4 Unplanned Lens Replacement

No spare lenses will be dispensed to the subject. If a lens is lost, damaged, or needs to be replaced due to a device deficiency/ADE, the subject will be instructed to return for an unplanned lens replacement. Refer to the MOP for details.

## 10.5 Discontinued Subjects

### 10.5.1 Screen Failures

Subjects who were excluded from the study after signing the informed consent and prior to randomization to product/dispense of study product are considered screen failures. The investigator must document the reason for screen failure in the subject's case history source documents.

Subject numbers must not be reused.

## 10.5.2 Discontinuations

Discontinued subjects are individuals who voluntarily withdraw or are withdrawn from the study by the investigator after signing informed consent and after randomization.

Subject numbers of discontinued subjects must not be reused (i.e., subject replacement is not allowed).

Subjects may discontinue from study or study treatment at any time for any reason. Subjects may also be discontinued from study treatment at any time if, in the opinion of the investigator, continued treatment poses a risk to their health.

If a subject discontinues from study treatment, every effort must be made to keep the subject in the study and to continue with the study assessments as specified in the schedule of study procedures and assessments until the final visit.

For subjects discontinuing from the study, the investigator must complete all Exit procedures according to [Table 3–1](#) and [Section 10.5.3](#), if the subject is willing and able, and if in the opinion of the investigator it is safe for the subject to do so.

The investigator must document the reason for study or treatment discontinuation in the subject's case history source documents.

To ensure the safety of all subjects who discontinue early, investigators must assess each subject and, if necessary, advise them of any therapies and/or medical procedures that may be needed to maintain their health.

## 10.5.3 Schedule of Procedures and Assessments for Subjects Discontinued from Investigational Product

Other than screen failures, if a subject discontinues from the study, the subject should undergo an Early Exit Visit. Refer to [Table 3–1](#) and the MOP for details.

## 10.6 Clinical Study Termination

The study sponsor reserves the right to suspend or close the investigational site or suspend or terminate the study in its entirety at any time.

If the clinical study is prematurely terminated or suspended by the study sponsor:

- The study sponsor must:

- o Immediately notify the investigator(s) and subsequently provide instructions for study termination.
- o Inform the investigator and the regulatory authorities of the termination/suspension and the reason(s) for the termination/suspension.
- The investigator must:
  - o Promptly notify the IRB/IEC of the termination or suspension and of the reasons.
  - o Provide subjects with recommendations for poststudy treatment options as needed.

The investigator may terminate the site's participation in the study for reasonable cause.

Breaking of the masked treatment codes will be done after locking the database.

### **10.6.1 Follow-up of Subjects after Study Participation has Ended**

Following this study, the subject will return to their eye care professional for their routine eye care.

[figure not shown]
## **11 ADVERSE EVENTS AND DEVICE DEFICIENCIES**

### **11.1 General Information**

An AE is any untoward medical occurrence, unintended disease or injury, or untoward clinical signs (including abnormal laboratory findings) in subjects, users, or other persons, whether or not related to the investigational medical device. Refer to the Glossary of Terms and the figures below for categories of AEs and SAEs.

[figure not shown]
**Figure 11-1**

**Categorization of All Adverse Events**

**Figure 11-2**

**Categorization of All Serious Adverse Events**

### **Specific Events Relevant to this Protocol**

#### ***Serious Adverse Events***

In addition to reporting all AEs (serious and nonserious) meeting the definitions, the investigator must report any occurrence of the following as an SAE:

- An ocular infection, including a presumed infectious ulcer with any of the following characteristics:
  - o Central or paracentral location

- o Penetration of Bowman's membrane
- o Infiltrates > 2 mm diameter
- o Iritis
- o Increase in intraocular pressure
- o Culture positive for microorganisms
- o Increasing size or severity at subsequent visits
- Any central or paracentral corneal event (such as neovascularization) that results in permanent opacification
- Hypopyon
- Hyphema
- Neovascularization within the central 6 mm of the cornea
- Permanent vision loss as defined by loss of 2 or more lines of BCVA from baseline visit that fails to resolve
- Uveitis (anterior, intermediate, or posterior)
- Corneal abrasion affecting  $\geq$  50% of corneal surface area

*Note: For cultured events, document available results in the narrative section(s) of the corresponding ADE-SAE eCRF.*

